8.2 Plasma protein binding

Selected plasma samples (described in the Schedule of Activities [Section 1.3]) will be collected and archived to measure the ex-vivo plasma protein binding of PSL and if feasible its metabolites [REDACTED]. If these investigations are performed, they will be described and reported as an attachment to the clinical study report (CSR).

8.3 Safety assessments

The safety and tolerability of SD and MD of PSL will be monitored by evaluation of AEs, clinical laboratory test results, vital signs (pulse rate, respiratory rate, SBP, DBP, and body temperature), 12-lead ECG parameters, Psychiatric and Mental Status and physical examination findings, and suicidal risk monitoring.

Planned time points for all safety assessments are provided in the Schedule of Activities ([Table 1-2](#)).

8.3.1 Clinical safety laboratory assessments

See Appendix 2 (Section 10.2) for the list of clinical laboratory tests to be performed and to the Schedule of Activities ([Table 1-2](#)) for the timing and frequency.

The Investigator must review the laboratory report, document this review, and record any clinically relevant changes occurring during the study in the AE section of the eCRF. The laboratory reports must be filed with the source documents. Clinically significant abnormal laboratory findings are laboratory findings that change considerably or their frequency or intensity increases more than expected as compared to the clinical profile known to the Investigator from the study participant's history or Screening Period.

All laboratory tests with values considered clinically significantly abnormal during participation in the study or at the EOT/EOS Visit should be repeated until the values return to normal or baseline or are no longer considered clinically significant by the Investigator or Medical Monitor.

If such values do not return to normal/baseline within a period of time judged reasonable by the Investigator, the etiology should be identified and the Sponsor notified.

All protocol-required laboratory assessments, as defined in Appendix 2 (Section 10.2), must be conducted in accordance with the Laboratory Manual and the Schedule of Activities (Table 1-2).

If laboratory values from non-protocol specified laboratory assessments performed at the institution's local laboratory require a change in study participant management or are considered clinically significant by the Investigator (eg, SAE or AE or dose modification), then the results must be recorded in the eCRF.

8.3.2 Vital signs

Body temperature, pulse rate, respiratory rate, and blood pressure will be assessed as outlined in the Schedule of Activities (Table 1-2).

Temperature may be measured by either oral or aural route at the discretion of the site, but must be performed using the same method in any individual study participant on all occasions.

Blood pressure measurements will be performed in both supine and standing positions for orthostatic measurement at Screening (supine BP after the study participant has been lying down for 5 minutes, then standing BP after 1 minute and 3 minutes), and in a supine position for routine blood pressure measurements at all assessments. Blood pressure and pulse measurements will be assessed with a completely automated device. Manual techniques will be used only if an automated device is not available.

Blood pressure and pulse measurements should be preceded by at least 5 minutes of rest for the study participant in a quiet setting without distractions (eg, television, cell phones).

Vital signs (to be taken before blood collection for laboratory tests) will consist of 1 pulse and 1 blood pressure measurement.

8.3.3 Electrocardiograms

Triplicate 12-lead ECG will be obtained as outlined in the Schedule of Activities (Table 1-2) using an ECG machine that automatically calculates the heart rate and measures PR, QRS, QT, and QTc intervals. Refer to Section 7 for QTc withdrawal criteria and any additional QTc readings that may be necessary.

All ECG recordings should be taken with the study participant resting in the supine position for at least ≥ 5 minutes before the recording.

At each time point at which triplicate ECG are required, 3 individual ECG tracings should be obtained as closely as possible in succession, but no more than 2 minutes apart. The full set of triplicates should be completed in less than 4 minutes.

8.3.4 Physical examination

Physical examinations will be performed at Screening and the time points specified in Section 1.3.

A complete physical examination will include, at a minimum, general appearance; ear, nose, and throat; eyes, hair, and skin; and assessments of the Cardiovascular, Respiratory, Gastrointestinal Neurological, Musculoskeletal, and Hepatic systems; and mental status. Height and weight will also be measured and recorded.

A brief physical examination will include, at a minimum, assessments of the skin, lungs, cardiovascular system, and abdomen (liver and spleen).

Investigators should pay special attention to clinical signs related to previous serious illnesses.

Clinically relevant findings or worsening of previous findings will be recorded as AEs.

8.3.5 Suicidal risk monitoring

Padsevonil is considered to be an AED. Suicidal ideation and behavior have been reported in patients treated with antiepileptic agents in several indications. A meta-analysis of randomized placebo-controlled studies of AEDs has also shown a small increased risk of suicidal ideation and behavior. The mechanism of this risk is not known and the available data do not exclude the possibility of an increased risk for PSL.

Suicidality will be assessed by trained study personnel using the C-SSRS (Columbia University Medical Center, 2008). This scale will be used for screening as well as to assess suicidal ideation and behavior that may occur during the study. All study participants will complete the “Screening” version of the C-SSRS at Visit 1 (assessing the past 6 months) and the “Baseline” Version of the C-SSRS at Visit 2, followed by the “Since Last Visit” version at the visits indicated on the Schedule of Activities (Table 1-2).

Study participants being treated with PSL should be monitored appropriately and observed closely for suicidal ideation and behavior or any other unusual changes in behavior. Families and caregivers of study participants being treated with PSL should be instructed to monitor study participants for the emergence of unusual changes in behavior, as well as the emergence of suicidal ideation and behavior, and to report such symptoms immediately to the study Investigator. Consideration should be given to discontinuing PSL in study participants who experience signs of suicidal ideation or behavior.

8.3.6 Psychiatric and Mental Status

The psychiatric and mental status of participating subjects will be closely monitored. Assessment of specific domains of psychiatric and cognitive symptoms will be performed by a staff member trained in the identification of psychiatric symptoms. The Psychiatric and Mental Status assessment will be performed at Baseline and all scheduled time points in the Schedule of Activities (Table 1-2). The parameters that will be evaluated are orientation, attention, memory, mood, calculus, behavior, and thinking or feeling. These parameters will be assessed as normal or abnormal and then determined whether clinically significant. If present and abnormal, psychiatric symptoms, mental impairment, and behavioral problems will be assessed as to whether they are clinically significant.

8.4 Adverse events

The definitions of an AE or SAE can be found in Appendix 3 (Section 10.3).

Adverse events will be reported by the study participant (or, when appropriate, by a caregiver, surrogate, or the study participant’s legally authorized representative).

The Investigator and any designees are responsible for detecting, documenting, and recording events that meet the definition of an AE or SAE and remain responsible for following up AEs that are serious, considered related to the study treatment or study procedures, or that caused the study participant to discontinue the PSL or UP0053 (see Section 7).

8.4.1 Time period and frequency for collecting AE and SAE information

All AEs and SAEs will be collected from the signing of the ICF and at the time points specified in the Schedule of Activities (Table 1-2).

Medical occurrences that begin before the start of study treatment but after obtaining informed consent will be recorded on the Medical History/Current Medical Conditions section of the eCRF, not the AE section.

All SAEs will be recorded and reported to the Sponsor or designee within 24 hours, as indicated in Appendix 3 (Section 10.3). The Investigator will submit any updated SAE data to the Sponsor within 24 hours of it being available.

The Investigator is specifically requested to collect and report to the Sponsor (or its representative) any SAEs (even if the Investigator is certain that they are in no way associated with the study medication), up to 30 days from the end of the study for each study participant, and to also inform study participants of the need to inform the Investigator of any SAE within this period. Serious AEs that the Investigator thinks may be associated with the study medication must be reported to the Sponsor regardless of the time between the event and the end of the study.

The method of recording, evaluating, and assessing causality of AE and SAE and the procedures for completing and transmitting SAE reports are provided in Appendix 3 (Section 10.3).

8.4.2 Method of detecting AEs and SAEs

Care will be taken not to introduce bias when detecting AEs and/or SAEs. Open-ended and non-leading verbal questioning of the study participant is the preferred method to inquire about AE occurrences.

8.4.3 Follow-up of AEs and SAEs

After the initial AE/SAE report, the Investigator is required to proactively follow each study participant at subsequent visits/contacts. All SAEs and non-serious AEs of special interest (AESIs) (as defined in Section 8.4.6) will be followed until resolution, stabilization, the Investigator determines that it is no longer clinically significant, the event is otherwise explained, or the study participant is lost to follow-up (as defined in Section 7.3). Further information on follow-up procedures is given in Appendix 3 (Section 10.3).

8.4.4 Regulatory reporting requirements for SAEs

Prompt notification by the Investigator to the Sponsor of a SAE is essential so that legal obligations and ethical responsibilities towards the safety of study participants and the safety of a study treatment under clinical investigation are met.

The Sponsor has a legal responsibility to notify both the local regulatory authority and other regulatory agencies about the safety of a study treatment under clinical investigation. The Sponsor will comply with country-specific regulatory requirements relating to safety reporting to the regulatory authority, IRB/IEC, and Investigators.

Investigator safety reports must be prepared for suspected unexpected serious adverse reactions according to local regulatory requirements and Sponsor policy and forwarded to Investigators as necessary.

An Investigator who receives an Investigator safety report describing a SAE or other specific safety information (eg, summary or listing of SAEs) from the Sponsor will review and then file it along with the IB and will notify the IRB/IEC, if appropriate, according to local requirements.

8.4.5 Pregnancy

Details of all pregnancies in female study participants and, if indicated, female partners of male study participants, will be collected after the start of study treatment and until 30 days after the birth for any significant medical issues. In certain circumstances, the Sponsor may request that follow up is continued for a period longer than 30 days. If the study participants is lost to follow up and/or refuses to give information, written documentation of attempts to contact the study participant needs to be provided by the Investigator and filed at the site. The Sponsor's Patient Safety (PS) department is the primary contact for any questions related to the data collection for the pregnancy, eventual birth, and follow up.

If a pregnancy is reported, the Investigator must immediately inform the Sponsor within 24 hours of learning of the pregnancy and should follow the procedures outlined in Appendix 4 (Section 10.4).

The study participant should be withdrawn from the study as soon as pregnancy is known (by positive pregnancy test), and the following should be completed:

- The study participant should return for the EOS/EOT Visit.
- The study participant should immediately stop the intake of the study medication or be tapered as instructed at the EOS/EOT Visit.

Abnormal pregnancy outcomes (eg, spontaneous abortion, fetal death, stillbirth, congenital anomalies, ectopic pregnancy) are considered SAEs.

8.4.6 Adverse events of special interest

An AESI is any AE that a regulatory authority has mandated be reported on an expedited basis, regardless of the seriousness, expectedness, or relatedness of the AE to the administration of a UCB product/compound. No AESIs have been identified for PSL to date, with the exception of potential Hy's Law as described below.

Potential Hy's Law, defined as $\geq 3 \times \text{ULN}$ ALT or AST with coexisting $\geq 2 \times \text{ULN}$ total bilirubin in the absence of $\geq 2 \times \text{ULN}$ ALP, with no alternative explanation for the biochemical abnormality, must ALWAYS be reported to the Sponsor as an AESI (ie, without waiting for any additional etiologic investigations to have been concluded). Follow-up information should then be reported if an alternative etiology is identified during investigation and monitoring of the study participant.

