7.1.1 Liver chemistry stopping criteria

Discontinuation of study medication for abnormal liver function should be considered by the Investigator when a study participant meets one of the conditions outlined in [Figure 7-1](#) or if the Investigator believes that it is in best interest of the study participant.

Study medication will be discontinued immediately and permanently for a study participant if liver chemistry stopping criteria are met.

Figure 7-1: Liver Chemistry Stopping Algorithm

Abbreviations: ALT=alanine aminotransferase; INR=international normalized ratio; SAE=serious adverse event; ULN=upper limit of normal.

Specific assessments and follow up actions for potential drug-induced liver injury are provided in [Appendix 6](#) (Section [10.6](#)).

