8 STUDY ASSESSMENTS AND PROCEDURES

Study procedures and their timing are summarized in the Schedule of Activities ([Table 1-2](#)).

Protocol waivers or exemptions are not allowed.

Immediate safety concerns should be discussed with the Sponsor immediately upon occurrence or awareness to determine if the study participant should continue or discontinue study treatment.

Adherence to the study design requirements, including those specified in the Schedule of Activities ([Table 1-2](#)), is essential and required for study conduct.

All Screening evaluations must be completed and reviewed to confirm that potential study participants meet all eligibility criteria. The Investigator will maintain a screening log to record details of all study participants screened and to confirm eligibility or record reasons for screening failure, as applicable.

Procedures conducted as part of the study participant's routine clinical management (eg, blood count) and obtained before signing of the ICF may be utilized for screening or baseline purposes provided the procedures met the protocol-specified criteria and were performed within the time frame defined in the Schedule of Activities ([Table 1-2](#)).

The maximum amount of blood collected from each study participant over the duration of the study, including any extra assessments that may be required, will not exceed 500mL. Repeat or unscheduled samples may be taken for safety reasons or for technical issues with the samples.

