
NOTES:
 
¹ Details of liver chemistry stopping criteria and required actions and follow-up assessments after liver stopping or monitoring event are given in Section 7.1.1 and Section 10.6, respectively. All events of ALT $\geq 3 \times \text{UL}$ and bilirubin $\geq 2 \times \text{ULN}$ ($>35\%$ direct bilirubin) or ALT $\geq 3 \times \text{ULN}$ and international normalized ratio (INR) >1.5, if INR measured, may indicate severe liver injury (possible Hy's Law) and must be reported as an SAE (excluding studies of hepatic impairment or cirrhosis).
	

This document cannot be used to support any marketing authorization application and any extensions or variations thereof.

REDACTED COPY

10.3 Appendix 3: Adverse events – definitions and procedures for recording, evaluating, follow-up, and reporting

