10.6 Appendix 6: Liver safety – suggested actions and follow-up assessments

Study participants with potential drug-induced liver injury must be assessed to determine if study medication must be discontinued. In addition, all concomitant medications and herbal supplements that are not medically necessary should also be discontinued.

Investigators should attempt to obtain information on study participants in the case of study medication discontinuation to complete the final evaluation.

Study participants with potential drug-induced liver injury should not be withdrawn from the study until investigation and monitoring are complete. All results of these evaluations and observations, as well as the reason(s) for study medication discontinuation and/or study participant withdrawal (if applicable), must be recorded in the source documents. The CRF must document the primary reason for discontinuation of study medication.

A specific monitoring plan must be agreed between the UCB Study Physician and the Investigator for study participants who have ALT >5 ULN. The monitoring plan should include any necessary follow-up assessments (until resolution of the abnormal lab values).

Phase 1 liver chemistry stopping criteria are designed to assure study participant safety and to evaluate liver event etiology (Table 10-2).

Table 10-2: Phase I liver chemistry stopping criteria and follow-up assessments

Liver Chemistry Stopping Criteria – Liver Stopping Event	
ALT-absolute	ALT ≥ 3xULN If ALT ≥ 3xULN AND bilirubin ≥ 2xULN (>35% direct bilirubin) OR international normalized ratio (INR) > 1.5, report as a serious adverse event (SAE). ^{a,b} See additional actions and follow-up assessments listed below
Suggested Actions and Follow up Assessments	
Actions	Follow Up Assessments

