
phosphatase, bilirubin) and perform liver event follow-up assessments within 24 hours.
 
• Monitor study participant twice weekly until liver chemistry test abnormalities resolve, stabilize, or return to baseline.• A specialist or hepatology consultation is recommended. 
If ALT $\geq 3xULN$ AND bilirubin $< 2xULN$ and INR ≤ 1.5:
 
• Repeat liver chemistry tests (include ALT, AST, alkaline phosphatase, bilirubin) and perform liver chemistry follow-up assessments within 24 to 72 hours.• Monitor study participants weekly until liver chemistry abnormalities resolve, stabilize, or return to baseline.	
• Record use of concomitant medications (including acetaminophen, herbal remedies, and other over-the-counter medications) on the concomitant medications eCRF.• Record alcohol use on the liver event alcohol intake eCRF. 
If ALT $\geq 3xULN$ AND bilirubin $\geq 2xULN$ or INR > 1.5:
 
• Anti-nuclear antibody, anti-smooth muscle antibody, Type 1 anti-liver kidney microsomal antibodies, and quantitative total IgG or gamma globulins.• Serum acetaminophen adduct high performance liquid chromatography assay (quantifies potential acetaminophen contribution to liver injury in study participants with definite or likely acetaminophen use in the preceding week [James et al, 2009].• Liver imaging (ultrasound, magnetic resonance, or computerized tomography) and/or liver biopsy to evaluate liver disease; complete liver imaging and/or liver biopsy CRFs.
---	--

^a Serum bilirubin fractionation should be performed if testing is available. If serum bilirubin fractionation testing is unavailable, record the absence/presence of detectable urinary bilirubin on dipstick, which is indicative of direct bilirubin elevations suggesting liver injury.

^b All events of ALT $\geq 3xULN$ and bilirubin $\geq 2xULN$ ($>35\%$ direct bilirubin) or ALT $\geq 3xULN$ and INR > 1.5 may indicate severe liver injury (possible 'Hy's Law') and must be reported as an SAE (excluding studies of hepatic impairment or cirrhosis). The INR measurement is not required and the stated threshold value will not apply to study participants receiving anticoagulants.

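### Potential Hy's Law is defined on ALT or AST, but the readable mandatory liver stop names ALT only, so an AST-plus-bilirubin case is stopped by judgement rather than by rule

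*Protocol*

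**What the plan says.** **Definition and reporting.** Protocol Section 8.4.6 sets four limbs for potential Hy's Law: ALT or AST ≥3×ULN, total bilirubin ≥2×ULN, no ALP ≥2×ULN, and no alternative explanation. A case "must ALWAYS be reported to the Sponsor as an AESI", before any work-up of the cause is finished. The section does not mention stopping treatment.

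**Stop.** Section 7.1.1 first asks the Investigator to consider discontinuation when a Figure 7-1 condition is met. It then says: "Study medication will be discontinued immediately and permanently for a study participant if liver chemistry stopping criteria are met". Table 10-2 (Section 10.6), titled as the stopping criteria, has one row, an absolute ALT of at least 3×ULN. Its SAE line begins "If ALT ≥ 3xULN AND bilirubin ≥ 2xULN (>35% direct bilirubin", again on ALT. Figure 7-1 is not shown; its abbreviation key covers ALT, INR, SAE and ULN.

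**SAE rule.** Table 10-2 footnote b says that ALT ≥3×ULN with raised bilirubin (more than 35% direct) or INR above 1.5 "must be reported as an SAE (excluding studies of hepatic impairment or cirrhosis". Note 1 in Appendix 2 gives the same ALT-based rule, with the INR limb qualified: "if INR measured, may indicate severe liver injury".

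**What else covers the case.** Section 10.6 opens with a duty to assess: "Study participants with potential drug-induced liver injury must be assessed to determine if study medication must be discontinued". Section 8.4.3 says that SAEs and non-serious AESIs "will be followed until resolution, stabilization, the Investigator determines that it is no longer clinically significant". Section 8 adds: "Immediate safety concerns should be discussed with the Sponsor immediately upon occurrence or awareness".

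**The concern.** The protocol uses one enzyme set to recognise its most serious liver signal and a narrower one to act on it. If AST and bilirubin rise together while ALT stays under 3×ULN, the event meets the sponsor's own definition of potential Hy's Law but does not trigger the stop. An ALT of 3×ULN with normal bilirubin, a weaker signal, does.

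The participants are healthy adults and elderly people who, by Section 2.3, receive no medical benefit. Section 4.3 expects that elderly exposure might be higher because of reduced hepatic function. In that setting, an event labelled potential Hy's Law would normally end dosing by rule. At stake is the safety of an individual participant, not the PK comparison.

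**Working it through.** No sample size or error rate is involved. The check has two parts: put one test case through each rule, then count the doses still scheduled.

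**Test case:** AST ≥3×ULN, ALT <3×ULN, total bilirubin ≥2×ULN, ALP <2×ULN, no other cause found.

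| Rule | Trigger | Result for the test case |
|---|---|---|
| 8.4.6 AESI | ALT or AST, with bilirubin | Met; reporting mandatory |
| 7.1.1 with Table 10-2 stop | ALT ≥3×ULN | Not met |
| Figure 7-1 | Not shown; key lists ALT, not AST | Unknown; key suggests ALT only |
| Footnote b and Appendix 2 note 1 (SAE) | ALT, with bilirubin or INR | Not met |
| 10.3.2 important medical event | Potential Hy's law named, no enzyme limit | Usually serious |
| 7.1 | Laboratory abnormality that the Investigator judges unsafe | Stop if so judged |
| 7.2 items 1 and 6 | Relevant medical condition; Sponsor or regulator request | Withdrawal if so judged or requested |
| 10.6 opening text | Potential drug-induced liver injury | Must be assessed; stop not prescribed |
| SAP 10.3 listing | ALT or AST ≥3×ULN | Listed |

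Swap the two enzymes and the same participant meets the Table 10-2 stop. No text explains the difference, and the SAP listing follows 8.4.6 rather than Table 10-2.

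**Scheduled doses from Day 8 (Section 4.1.2):**

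2×50 + 2×100 + 6×200 + (200 + 100) + 4×100 + 2×50 = 2300 mg, in 2 + 2 + 6 + 2 + 4 + 2 = 18 doses.

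Table 1-2 places post-dose chemistry on Days 4, 8, 13, 16 and 22, before the morning dose on dosing days. Laboratory turnaround is not given. I assume that the result is known at some point between just before that morning's dose and just before the next morning's dose.

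| Result from | Doses left | mg left | Arithmetic |
|---|---|---|---|
| Day 4 | 18 | 2300 | no dose due before Day 8 |
| Day 8 | 16 to 18 | 2200 to 2300 | 2300 − 2×50 = 2200 |
| Day 13 | 6 to 8 | 500 to 800 | 200 + 100 + 400 + 100 = 800; 800 − 300 = 500 |
| Day 16 | 0 to 2 | 0 to 100 | 2×50 = 100; 100 − 100 = 0 |
| Day 22 | 0 | 0 | dosing over |

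Of the 8 doses after a Day 13 morning result, 7 are step-down doses: 100 + 4×100 + 2×50 = 600 of the 800 mg.

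**The case against.** The strongest reply has five parts.

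- **The figure is missing.** Section 7.1.1 refers to Figure 7-1, and its absence from this copy is not a fault of the plan. That stands. The abbreviation key points to ALT only but does not prove it. If the figure does include AST, the stop exists there and Table 10-2 needs to be brought into line with it.
- **Different jobs.** An expedited-reporting definition and a stopping rule need not match, and Table 10-2 is stricter in one respect because ALT alone triggers it. True, but that does not explain why the combined AST case is left out.
- **The case is already handled.** Sections 7.1, 7.2 (items 1 and 6) and 10.6 allow a stop. Section 4.1.2 sends dosing decisions to the sponsor's study physician first. Section 8.3.1 calls for clinically significant abnormal tests to be repeated, and Sections 9.7 and 10.1.5 provide a Safety Monitoring Committee. These safeguards are real and make the gap narrow. None of them makes the stop automatic.
- **The dose counts exaggerate.** Eighteen doses would require the Investigator and an informed Sponsor to begin multiple dosing with an open AESI, despite another pre-dose panel on Day 8. This stands: the counts are ceilings, not expected exposure.
- **Stopping has a cost.** Section 2.3 reports acute psychiatric events in two healthy participants soon after untitrated start or untapered cessation, and Section 7.2 prefers a taper where possible. This also stands, although the protocol already accepts an immediate stop for ALT ≥3×ULN alone.

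A reader might infer that such a case could go unreported. The documents do not support that. AESI reporting is unconditional, follow-up is required, and Section 10.3.2 lists potential Hy's law as usually serious. A reader might also infer that treatment would continue. The documents leave that to judgement; they do not direct it.

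**Conclusion.** The mismatch is real on the readable text, and it is narrow. It concerns the automatic stop only: one enzyme pattern that the protocol itself calls potential Hy's Law is stopped by Investigator and Sponsor judgement, while its ALT counterpart is stopped by rule. The difference in SAE wording is close to moot.

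The documents give no probability. It should be low, because exclusion criterion 14 bars ALT, AST or ALP above 1.0×ULN. One qualification applies: criteria 15 and 16 admit Gilbert's syndrome and isolated raised bilirubin with direct bilirubin under 35%, with no stated upper limit. Such a participant may already be near the bilirubin limb at entry.

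The conclusion assumes that Figure 7-1 does not add AST. The dose ranges also rest on the assumed laboratory turnaround. The PK conclusions do not change. This is an inexpensive improvement to participant protection, not a defect that threatens the study.

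**What to change.** Keep ALT ≥3×ULN as the only single-enzyme stop.

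- **Table 10-2 stopping row, and Figure 7-1 if it reads ALT only.** Add: *or AST ≥3×ULN with total bilirubin ≥2×ULN (>35% direct bilirubin) and ALP <2×ULN (potential Hy's Law, Section 8.4.6), without waiting for etiologic work-up*.
- **Table 10-2 monitoring.** Give this case the same monitoring as the matching ALT-plus-bilirubin case.
- **Footnote b and Appendix 2 note 1.** Write *ALT or AST* for the bilirubin limb, keep the >35% direct-bilirubin condition for both enzymes, and leave the INR limb on ALT.

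The direct-bilirubin condition keeps a participant with Gilbert's syndrome and an incidental AST rise from being stopped by rule. That case can still be an AESI under 8.4.6.

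No new samples are needed, because AST, ALP and total and direct bilirubin are already in the Appendix 2 panel. The SAP needs no change.

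There are two downsides. A rare case later explained by another cause would be stopped for good, since Section 7.1 allows no restart. If stopped before the Day 13 profile, that participant would have no multiple-dose PK data, and replacement is discretionary under Section 7.2. An immediate stop also forgoes the taper used to limit psychiatric events.
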